6.4 Protecting Against or Minimizing Potential Treatment Risks

Subjects will not be enrolled who have other active serious medical problems. Frequent monitoring of patients with history, physical examination, and laboratory studies will allow for early identification of adverse events. All participants will be required to have adequate hemoglobin to allow safe frequent venipuncture. Every attempt will be made to minimize the number of venipunctures.

All study drug infusions and injections will take place in a facility that has resuscitation capabilities, and subjects will be closely monitored during and after the injection.

Subjects will be counseled about the potential risk for infections and the need to report any change in health status between or at the time of visits. Directed questioning about concurrent illness will occur before each injection. No injection will occur in those with signs or symptoms indicative of active infection.

7 ADVERSE EVENT REPORTING AND SAFETY MONITORING

7.1 Adverse Event Definition

7.1.1 Adverse Event

In this clinical trial, an adverse event is any occurrence or worsening of an undesirable or unintended sign, symptom or disease whether or not associated with the treatment and study procedures.

Throughout the study, the investigator must record all adverse events on source documents. Events not related hypoglycemia, or hyperglycemia which are Grade 2 or greater per the NCI CTCAE (see Section 7.1.5. Grading Event Severity below) must be reported to TNCC as AE. The investigator should treat participants with adverse events appropriately and observe them at suitable intervals until the events resolve or stabilize.

Adverse events may be discovered through:

- observation of the participant;
- questioning the participant;
- unsolicited complaint by the participant.

Questioning of the participant should be conducted in an objective manner.

7.1.2 Adverse Reaction

An adverse reaction means any adverse event caused by a drug. Adverse reactions are a subset of all suspected adverse events for which there is reason to conclude that the drug caused the event. Suspected adverse reaction means any adverse event for which there is a reasonable possibility that the drug caused the adverse event. For the purposes of safety reporting, “reasonable possibility” means there is evidence to suggest a causal relationship between the drug and the adverse event. A suspected adverse reaction implies a lesser degree of certainty about causality than an adverse reaction, which means any adverse event caused by a drug. Examples of evidence that suggest a causal relationship (reasonable possibility) between the drug and the adverse event include:

- A single occurrence of an event that is uncommon and known to be strongly associated with drug exposure
- One or more occurrences of an event that is not commonly associated with drug exposure, but is otherwise uncommon in the populations exposed to the drug
- An aggregate analysis of specific events observed in a clinical trial (such as known consequences of the underlying disease or condition under investigation or other events that commonly occur in the study population independent of drug therapy) that indicates those events occur more frequently in the drug treatment group than in a concurrent or historical control group.

7.1.3 Serious Adverse Event/Reaction

A serious adverse event (SAE) or reaction is defined as “any adverse event occurring at any dose that suggests a significant hazard, contraindication, side effect, or precaution.” An adverse event or suspected adverse reaction is considered “serious” if, in the view of either the investigator or sponsor, it results in any of the following outcomes:

1. Death. A death that occurs during the study or that comes to the attention of the investigator during the protocol-defined follow-up after the completion of therapy must be reported whether it is considered to be treatment related or not.
2. A life-threatening adverse event. A life-threatening event is any adverse therapy experience that, in the view of the investigator, places the participant at immediate risk of death from the reaction as it occurred.

3. Inpatient hospitalization or prolongation of existing hospitalization with the exception of hospitalization relating to initial diagnosis of type 1 diabetes.
4. Persistent or significant incapacity or substantial disruption of the ability to conduct normal life functions
5. Congenital anomaly or birth defect.
6. Important medical events that may not result in death, be life-threatening, or require hospitalization may be considered serious when, based upon appropriate medical judgment, they may jeopardize the patient or subject and may require medical or surgical intervention to prevent one of the outcomes listed above.

An adverse event or suspected adverse reaction is considered “life-threatening” if, in the view of either the investigator or sponsor, its occurrence places the patient or subject at immediate risk of death. It does not include an adverse event or suspected adverse reaction that, had it occurred in a more severe form, might have caused death.

Regardless of the relationship of the adverse event to study drug, the event must be reported as a serious adverse event if it meets any of the above definitions.

7.1.4 Unexpected Adverse Event

An adverse event/reaction is considered unexpected when the nature (specificity) or severity of the event is not consistent with the risks described in the Investigator’s Brochure or the informed consent document. Unexpected refers to an experience that has not been previously observed. This includes events that occur more frequently than expected.

7.1.5 Grading Event Severity and Causality

TrialNet has adopted usage of the National Cancer Institute (NCI) Common Technology Criteria for Adverse Events (CTCAE) and/or study-specific criteria for classification to describe the severity of adverse events with the exception of hypoglycemia and hyperglycemia. Hypoglycemia and hyperglycemia will be reported as adverse events only in the case of requiring the assistance of others due to loss of consciousness or DKA. TrialNet Investigators will also provide an assessment of relationship of AE to study drug as not, unlikely, possibly, probably, or definitely related.

7.2 Adverse Event Reporting and Monitoring

Adverse events will be reported to the TrialNet Coordinating Center. The investigator will grade their severity according to common toxicity criteria or study-specific criteria and will make a determination of their relation to therapy. Events will be assessed and reported consistent with the ICH Guideline for Good Clinical Practice, 21 CFR 312.32 for expedited safety reporting, and per the guidance of the DHHS Office for Human Research Protections (OHRP).

The adverse event case report form for the protocol must be completed for all adverse events (AE). For reporting serious adverse events (SAE), the MedWatch Form should also be completed and faxed to the TNCC *within 24 hours of when the site was notified of the event*. This will be reviewed by the TrialNet Medical Monitor, the TrialNet Safety Monitoring Committee, and the DSMB as appropriate. Deaths must be reported immediately. Event outcome and other follow-up information regarding the treatment and resolution of the event will be obtained and

reported when available, if not known at the time the event is initially reported. The follow-up information should contain sufficient detail to allow for a complete medical assessment of the case and an independent determination of possible causality.

Adverse events will be assessed by the TrialNet Medical Monitor. The DSMB will conduct regular safety reviews approximately every three to six months (and otherwise as needed) of adverse events by treatment group assignment. Serious adverse events as well as adverse events leading to study discontinuation will be reviewed by the DSMB.

For SAEs that are unexpected and considered possibly or probably drug related, the Medical Monitor will provide information on frequency of similar events, and generate FDA form 3500A reports (MedWatch form) for distribution to FDA, NIDDK, DSMB and site investigators. Expedited safety reports will be submitted to the IND by the NIDDK. The TNCC will also be primarily responsible for sending required safety information to Amgen.

8 STATISTICAL CONSIDERATIONS AND ANALYSIS PLAN

Analyses of study data will be conducted to address all objectives of the trial and other interrelationships among data elements of interest to the investigators and of relevance to the objectives of the study. Analyses by gender and race/ethnicity, as appropriate, are also planned.

Primary analysis of treatment effect will be conducted employing the intention-to-treat principle where all participants with measured one-year C-Peptide AUC mean are included regardless of treatment compliance (Complete Case Analysis).

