5.4 Metabolic Outcome Assessments

Metabolic assessments will consist of:

- Glucose records and reports of hypoglycemia

- Insulin dose
- HbA1c
- Mixed meal tolerance test (MMTT): 2 hour MMTT at 3, 6, 9 months, 4 hour MMTT at screening, 12, 18, and 24 months

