5.6 Withdrawal from treatment

The study will be conducted according to the intent-to-treat principle. This means that once randomized into the study, a participant will be expected to undergo all scheduled follow-up assessments and will remain within the assigned treatment group for purposes of statistical analysis regardless of the actual course of treatment administered. Withdrawal from treatment does not automatically entail withdrawal from the study. Withdrawal from the study will only occur if the participant dies or withdraws consent. Subjects who withdraw consent are classified as inactive but may again become active upon re-entry into the study, if they so choose.

Withdrawal from treatment can occur for a number of reasons, some of which are outlined below.

A participant may elect to discontinue study medications, may be unable to continue them, or may be withdrawn (temporarily or permanently) at the discretion of the Principal Investigator if s/he determines that it is unsafe to continue or there is a significant change in the risk/benefit.

Non-pregnant individuals who are withdrawn from treatment should remain in the study and undergo scheduled assessment visits as appropriate and any additional visits as needed to address ongoing AEs. MMTT tests will not occur while an individual is pregnant.

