8.1 Primary Outcome and Analyses

The primary outcome of each participant is the area under the stimulated C-peptide curve (Y_{AUC}) over the first 2 hours of a mixed meal glucose tolerance test conducted at the one-year visit. The Y_{AUC} is computed using the trapezoidal rule which translates into a weighted sum of the timed C-peptide values over the 120 minute MMTT. The more appealing quantity is the AUC mean which is $\frac{Y_{AUC}}{120}$ in nmol/L and will be denoted as Y_{Cp} .

Let $Y_{Cp}^{ATG/GCSF}$, Y_{Cp}^{ATG} , and $Y_{Cp}^{Control}$ represent the C-peptide AUC mean for study patients receiving both ATG and GCSF, receiving ATG alone, and those receiving placebo, respectively. Likewise, let $\mu_{Cp}^{ATG/GCSF}$, μ_{Cp}^{ATG} , and $\mu_{Cp}^{Control}$ represent the population mean of C-Peptide for these groups at one year, respectively.

The primary statistical hypotheses to be assessed in the study are:

$$H_0: \mu_{Cp}^{ATG/GCSF} = \mu_{Cp}^{Control} \text{ versus } H_a: \mu_{Cp}^{ATG/GCSF} > \mu_{Cp}^{Control}$$

$$H_0: \mu_{Cp}^{ATG} = \mu_{Cp}^{Control} \text{ versus } H_a: \mu_{Cp}^{ATG} > \mu_{Cp}^{Control}$$

The primary analysis will be conducted on a transformed scale using the function $\log(Y_{Cp} + 1)$. This provides better normal distributional behavior by the test statistic. The comparison between any two treatment arms will be based on a Wald test of treatment effect in an ANCOVA model adjusting for gender, baseline age, and baseline $\log(Y_{Cp} + 1)$.

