8.4 Sample Size and Power Calculations

The primary analysis will compare the difference in C-Peptide between experimental and placebo treatment groups at 12 months using $\log(Y_{Cp} + 1)$ transformation and ANCOVA model adjusting for gender, baseline age and the baseline value of $\log(Y_{Cp} + 1)$. Estimates of the mean and standard deviation of $\log(Y_{Cp} + 1)$ (expressed algebraically as: $\hat{\mu}_{\log(Y_{Cp} + 1)}$ and $\hat{\sigma}_{\log(Y_{Cp} + 1)}$) in the placebo group were derived from the last four TrialNet studies of early onset disease. The 90% confidence bound estimates were used to provide good confidence that this trial's study population characteristics fall within these limits to assure the advertised statistical power; the estimates are $\hat{\mu}_{\log(Y_{Cp} + 1)} = 0.360$ and $\hat{\sigma}_{\log(Y_{Cp} + 1)|X} = 0.167$ (i.e., the residual mean squared error regressing on gender, baseline age and C-peptide). The geometric-like mean of Y_{Cp} for the placebo group is $\exp(0.36) - 1 = 0.433$ nmol/L.

Using standard equations for the comparison of two means and a 1:1:1 allocation, a sample size of 78 participants (26 per group) with complete data would provide power of 85% to detect a 50% increase in the geometric-like mean in either experimental treatment group (compared to the control) using the Wald test (from the adjusted linear model) at the 0.025 level (one-sided). Thus the overall Type I error for both tests is approximately 0.05.

Assuming that 10% of the participants will have missing data (one-year MMTT was not done or subject withdrew prior to the one-year assessment), the sample size goal for this study will be set at 84 participants (28 per group).

The study will be closed to additional participants when the total number then randomized plus a fraction of those in screening (i.e., screening for eligibility) is expected to provide the proper number of eligible participants. Participants who had already conducted the initial screening visit at that time will be allowed to complete screening and be randomized if both consenting and eligible.

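### The primary analysis is called intention-to-treat but is a 12-month complete-case ANCOVA that leaves earlier C-peptide values of those lost unused; a cheap improvement is available

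*Protocol*

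**What the plan says.** The opening of Section 8 invokes intention-to-treat for the primary analysis and then defines who enters it: "all participants with measured one-year C-Peptide AUC mean are included regardless of treatment compliance (Complete Case Analysis". The wording covers non-compliance with treatment; it does not cover an outcome that was never measured.

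Section 8.1 fixes the model at one time point: "The comparison between any two treatment arms will be based on a Wald test of treatment effect in an ANCOVA model adjusting for gender, baseline". The covariate list, cut short here, holds only sex and two values taken at entry (how old the participant is, and C-peptide). No post-baseline value before month 12 enters it. Section 8.6 uses the same model for the interim efficacy and futility tests.

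Section 5.6 describes intention-to-treat in terms of assigned group: a randomised participant "will remain within the assigned treatment group for purposes of statistical analysis regardless of the actual course of treatment administered". It also names one planned reason for a missing test: "MMTT tests will not occur while an individual is pregnant".

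Section 5.4 schedules the C-peptide tests: "2 hour MMTT at 3, 6, 9 months, 4 hour MMTT at screening, 12, 18, and 24 months". The values from months 3, 6 and 9 appear only in secondary analyses (Section 8.2). These are ANCOVAs by visit and a mixed model with random intercept and slope that compares mean intercepts and slopes between arms.

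Section 8.4 expects 10% of participants to lack the one-year result and sets enrolment at 84 for that reason.

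**The concern.** Whether a participant is analysed depends on something that happens after randomisation, namely having the 12-month MMTT. Randomisation protects the comparison of everyone assigned; it does not automatically protect the comparison of those who are measured at one year. Infusion reactions and serum sickness are expected with ATG (Sections 4.6 and 4.7.3) and bone pain with GCSF (Section 6.2.2), so loss that differs by arm is conceivable. Such effects may also hint at assignment and lead placebo participants to leave. The bias could run in either direction.

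At stake are the two confirmatory contrasts, each tested one-sided at 0.025. The data that would lessen the problem, up to three earlier measurements of the same endpoint per participant, are already collected. The secondary mixed model does not fill the gap, because it compares intercepts and slopes over months 3 to 24 rather than the 12-month difference.

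This is not detail left to a statistical analysis plan: the protocol itself states both the analysis set and the model.

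**Working it through.** **Inputs from the protocol (Section 8.4).** Control mean 0.360 and residual SD 0.167 on the log(Y_Cp + 1) scale; a 50% increase in the geometric-like mean; one-sided 0.025 per comparison; 26 complete per group for 85% power; 10% missing; 28 randomised per group.

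**Step 1: reproduce the design.**
- Design effect: ln(1 + 1.5 × (exp(0.36) − 1)) − 0.36 = ln(1.65) − 0.36 = 0.141.
- n per group = 2 × (1.960 + 1.036)² × (0.167 / 0.1408)² = 25.3, rounded up to 26. This matches the protocol.
- Power at 26 per group is 86.0% by the normal formula and 85.0% by the noncentral t. The stated 85% is reproduced.

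**Step 2: power under the complete-case rule (normal formula).**
- 10% loss leaves 28 × 0.9 = 25.2 per arm.
- SE = 0.167 × √(2 / 25.2) = 0.0470; 0.1408 / 0.0470 = 2.99; power = Φ(2.99 − 1.96) = 84.9%.
- With nothing missing (28 per arm), power is 88.4%.

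**Step 3: what earlier data could recover.** The variance of an arm mean when a 9-month value is used is SD² × [(1 − ρ²) / n₁₂ + ρ² / n₉]. Here n₁₂ is the number with a 12-month value, n₉ the number with a 9-month value, and ρ the residual 9-to-12-month correlation. The protocol gives neither ρ nor the share of lost participants with a 9-month value, so both are assumed.
- ρ = 0.5, half of those lost have a 9-month value: 0.75 / 25.2 + 0.25 / 26.6 = 0.03916, an effective n of 25.5 and power of 85.4%.
- ρ = 0.9, all of those lost have one: 0.19 / 25.2 + 0.81 / 28 = 0.03647, an effective n of 27.4 and power of 87.7%.
- Gain over 84.9%: about 0.5 to 2.8 points. At 20% loss, complete-case power is 80.5% and the range using 9-month values is 81.6% to 86.9%.

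**Step 4: bias of the contrast.** Suppose a fraction d of an arm is missing and those participants average k residual SDs below their full arm mean. The observed arm mean is then too high by d × k × 0.167 / (1 − d). The bias of the contrast is the active-arm term minus the placebo term. All values of d by arm and of k are assumptions.

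| Missing, active v placebo | k | Bias | Share of 0.141 | One-sided type I error |
|---|---|---|---|---|
| 10% v 10% | same in both arms | 0 | 0% | 0.025 |
| 15% v 5% | 0.5 | +0.010 | 7% | 0.041 |
| 15% v 5% | 1 | +0.021 | 15% | 0.064 |
| 5% v 15% | 1 | −0.021 | −15% | 0.008 (power 72%) |

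Third row in full: (0.15 / 0.85 − 0.05 / 0.95) × 0.167 = 0.1238 × 0.167 = 0.0207. With 23.8 and 26.6 observed, SE = 0.167 × √(1 / 23.8 + 1 / 26.6) = 0.0471. The type I error is 1 − Φ(1.960 − 0.0207 / 0.0471) = 1 − Φ(1.521) = 0.064.

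**Step 5: would the earlier values repair it?** In a simulation (8,000 runs per scenario, ρ of 0.7 and 0.85), missingness depended on the 9-month value, with about 19% lost on active and 4.5% on placebo. Complete-case bias was +0.015 to +0.018 and type I error 0.050 to 0.063. Using the 9-month value, bias was about zero and type I error 0.028 to 0.030. With equal loss, complete-case type I error in the same simulation was 0.027 to 0.029, so the excess over 0.025 in the corrected analysis comes largely from using a normal critical value in small samples. The repair works here because missingness was made to depend on an observed value.

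**The case against.** The case for leaving the plan as it is has real substance.

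- **Retention.** Those who stop study treatment stay in the trial for all efficacy assessments (Section 4.7.2). Leaving the study requires death or withdrawn consent, and return is encouraged (Sections 5.6 and 5.7). Toxicity alone therefore does not create a missing MMTT.
- **Burden.** All three arms have two infusions and six injections (Sections 4.1 and 4.8.1), so visit and injection load does not separate the arms. Only the reactions may.
- **Pregnancy.** The rule on MMTTs has no stated link to arm, and participants are asked to avoid pregnancy to month 24 (Section 6.3).
- **Openness.** The protocol itself calls the analysis complete-case and enlarges the sample for loss.
- **The alternative.** A repeated-measures model relies on missing-at-random, which cannot be verified, and gains nothing from participants without any post-baseline value.

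These points stand, and they limit how serious the matter is. They do not change the fact that the stated rule excludes participants on a post-randomisation event and leaves their earlier measurements out of the primary test.

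A reader might infer three stronger things. First, that the primary result will be biased: nothing in the protocol shows unequal, outcome-related loss, and equal loss with equal deviation gives zero bias in the contrast. Second, that power is inadequate: 84.9% is essentially the stated 85%. Third, that Section 8 flatly contradicts Section 5.6: the latter promises analysis in the assigned group whatever treatment was received, not analysis of unmeasured outcomes. The fault there is a loose label.

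**Conclusion.** The point holds as an inexpensive improvement to the primary analysis, not as an error that invalidates it. The protocol presents a complete-case analysis as intention-to-treat and does not use relevant data already collected.

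The bias figures of 7% to 15% of the design effect, with one-sided type I error of 0.041 to 0.064, belong to one assumed pattern: 15% v 5% loss and a shortfall of 0.5 to 1 residual SD. The reverse imbalance at 1 SD would instead lower power to 72%. Bias needs both a link between loss and 12-month C-peptide, given arm and covariates, and a difference between arms in how many are lost or how far they lie from their arm mean. The power argument is minor on its own. Absence of a missing-not-at-random sensitivity analysis is not part of the finding, since that may sit in a statistical analysis plan that is not shown.

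**What to change.** Estimate the 12-month contrasts in all randomised participants, by one of two routes fixed before unblinding:

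1. Multiple imputation of missing 12-month log(Y_Cp + 1) from arm, gender, baseline age, baseline log(Y_Cp + 1) and the values at months 3, 6 and 9, followed by the ANCOVA already specified in Section 8.1.
2. A repeated-measures model on log(Y_Cp + 1) at months 3, 6, 9 and 12, with visit as a category, arm-by-visit terms and the same baseline covariates, testing the 12-month contrasts.

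Keep the complete-case ANCOVA as a sensitivity analysis. Reword the opening of Section 8 so that complete-case analysis is no longer presented as the intention-to-treat analysis.

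The cost is wording and programming; no visit or sample is added. The primary analysis becomes slightly more complex and rests on missing-at-random. The first route disturbs the plan least, because the analysis model stays as written. If the second is chosen, the selection rule (Section 8.4), the variance re-estimation (Section 8.5) and the information fractions counted in one-year completers (Section 8.6) must be brought into line with the new model.
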